9.3. Variables

Baseline variables during the 6 months prior to, and on, the index date will be measured. Baseline variables will be evaluated using codes in any position unless noted otherwise.

Table 1. Baseline Demographic and Clinical Characteristic Variables

Variable	Data Source(s)	Operational Definition
Age	Both VA and Medicare	Age will be defined as of the index date and used to assign patients to age groups (eg, 18-54, 55-64, 65-74, 75-79, \geq 80 years).
Sex	Both VA and Medicare	A flag will be created for female beneficiaries and reported as a percentage.
US Geographic Region	Both VA and Medicare	The United States will be divided into 5 regions: Northeast, South, Midwest, West, and Other.
Race	Both VA and Medicare	Race will be identified and will be categorized as: White, Black, Other, and unknown.
Year of index OAC	Both VA and Medicare	A flag will be created for proportion of unique patients with index OAC identified in 2013, 2014, 2015, 2016, and 2017.

Variable	Data Source(s)	Operational Definition
Dose of Index DOAC	Both VA and Medicare	-Standard dose (apixaban 5 mg, dabigatran 150 mg, and rivaroxaban 20 mg) based on dose of the initial prescription of DOAC; -lower dose (apixaban 2.5 mg, dabigatran 75 mg, rivaroxaban 15 mg/10 mg) based on dose of the initial prescription of DOAC.
Body Weight	VA	Body weight will be obtained as continuous and categorical variables. The categories will be: ≤ 60 kg, 61-99 kg, 100-119 kg, and ≥ 120 kg. If a patient has multiple values, the value closest to the index date will be used.
BMI	VA	Body Mass Index: Body mass index will be calculated as weight in kilograms divided by the square of height in meters. Mean, median, and standard deviation will be provided for the continuous variable. The categories will be <18.5 , 18.5-24.9, 25-29.9, 30-39, and ≥ 40 . If a patient has multiple values, the value closest to the index date will be used.
Creatinine Clearance	VA	Creatinine Clearance: Creatinine clearance will be identified using LOINC codes (2160-0, 33914-3, 48642-3, 48643-1, 62238-1, 2164-2, 14682-9). A categorical variable for the glomerular filtration rate (GFR) will be created with the following cutoff points: <15 ml/min, 15-29 ml/min, 30-59 ml/min, 60-89 ml/min, and ≥ 90 ml/min. If a patient has multiple values, the value closest to the index date will be used. The creatinine clearance rate (CrCl) will be calculated based on serum creatinine for patients who only had serum creatinine information. ²⁵

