INR	VA	International Normalized Ratio Test Results will be identified using Logical Observation Identifiers Names and Codes (LOINC; 34714-6, 38875-1, 46418-0, 52129-4, 5895-7, 5896-5, 61189-7, 6301-6, 72281-9) occurring anytime during the baseline period will be evaluated.
CHADS₂ Score	Both VA and Medicare	CHADS ₂ Score will be calculated according to the points algorithm outlined in Appendix Table 5 .

Variable	Data Source(s)	Operational Definition
CHA2DS₂-VASc Score	Both VA and Medicare	CHA2DS ₂ -VASc score will be calculated according to the points algorithm outlined in Appendix Table 6 .
HAS-BLED Score	Both VA and Medicare	HAS-BLED score will be calculated according to the points algorithm outlined in Appendix Table 7 .
Baseline Medication Use	Both VA and Medicare	A flag will be created for the following medications prescribed during the baseline period: angiotensin-converting enzyme inhibitors/ angiotensin-receptor blockers, aspirin, beta blockers, statins, proton pump inhibitors, H ₂ -receptor antagonists, antiplatelets, nonsteroidal anti-inflammatory drugs, inhibitors of warfarin, inducers of warfarin, dronedarone, digoxin, calcium channel blockers, renin angiotensin system antagonists, glucocorticoids, diuretics, metformin, sulfonylureas, thiazolidinedione, insulin, other diabetes drugs, antiulcer agents, and antidepressants (See Appendix Table 8 for codes).
Bariatric Surgery	Both VA and Medicare	A flag will be created for patients with claims for bariatric surgery (See Appendix Table 9 for codes).
CCI	Both VA and Medicare	Charlson Comorbidity index will be calculated as a continuous variable (See Appendix Table 10 for calculation and codes).
Comorbid Conditions	Both VA and Medicare	The following comorbid conditions will be flagged in baseline: History of stroke/SE, history of bleeding, myocardial infarction, renal disease, liver disease, dyspepsia or stomach discomfort, diabetes, hypertension, congestive heart failure, non-stroke/SE peripheral vascular disease, anemia and coagulation defects , transient ischemic attack, coronary artery disease, peripheral artery disease (See Appendix Table 11 for codes).

Table 2. Clinical and Outcome Variables

Variable	Data Source(s)	Operational Definition

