Major Bleeding Event	Both VA and Medicare	Major bleeding event(s) observed during follow-up will be identified using hospital claims which had a MB diagnosis as the primary diagnosis code and occurring anytime during the follow-up period of drug use or within 30 days from the last day of supply of treatment prescription. A major bleeding event will be a dichotomous variable that equals 1 if there is ≥ 1 bleeding event during the follow-up period. Time to the first major bleeding event will be calculated. The first major bleeding event will be stratified by gastrointestinal (GI), intracranial hemorrhage (ICH), and other MB. (See Appendix Table 12 for codes).
Stroke/SE Event	Both VA and Medicare	Stroke/SE will be identified using hospital claims which had a stroke/SE diagnosis code as the primary diagnosis code and occurring anytime during the period of drug use or within 30 days from the last day of supply of treatment prescription. Stroke/SE will be a dichotomous variable that equals 1 if there is ≥ 1 stroke event during the follow-up period. Time to the first stroke/SE event will be calculated. The first stroke/SE event will be stratified by ischemic stroke, hemorrhagic stroke, and SE. (See Appendix Table 12 for codes).
Net Clinical Benefit	Both VA and Medicare	For patients with stroke/SE OR MB event, net clinical benefit will be assessed by evaluating the first hospital claim for a stroke/SE or MB event. The hospital claim can occur anytime during the period of drug use or within 30 days from the last day of supply of treatment prescription.
INR	VA	International Normalized Ratio Test Results will be identified using Logical Observation Identifiers Names and Codes (LOINC; 34714-6, 38875-1, 46418-0, 52129-4, 5895-7, 5896-5, 61189-7, 6301-6, 72281-9) occurring anytime during the period of drug use or within 30 days from the last day of supply of treatment prescription. The mean

Variable	Data Source(s)	Operational Definition
		and median number of INR tests for warfarin patients will be calculated. The distribution of INR values (mean, median, maximum, minimum, Q1, Q3) will be evaluated descriptively and flags will be created for INR <2, 2-3, and >3.

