Hypertension	1 point	401.xx-405.xx	I10, I110, I119, I120, I129, I130, I1310, I1311, I132, I150, I151, I152, I158, I159, I160, I161, I169, N262
Abnormal kidney and/or liver function:	1 point each	Kidney: 580.xx-589.xx	B520, E0821, E0822, E0829, E0921, E0922, E0929, M3214, M3215, M3504, N000, N001, N002, N003, N004, N005, N006, N007, N008, N009, N010, N011, N012, N013, N014, N015, N016, N017, N018, N019, N020, N021, N022, N023, N024, N025, N026, N027, N030, N031, N032, N033, N034, N035, N036, N037, N038, N039, N040, N041, N042, N043, N044, N045, N046, N047, N048, N049, N050, N051, N052, N053, N054, N055, N056, N057, N058, N059, N060, N061, N062, N063, N064, N065, N066, N067, N068, N069, N070, N071, N072, N073, N074, N075, N076, N077, N078, N079, N08, N140, N141, N142, N143, N144, N150, N158, N159, N16, N170, N171, N172, N178, N179, N181, N182, N183, N184, N185, N186, N189, N19, N250, N251, N2581, N2589, N259, N261, N269, N270, N271, N279
Age ≥75 years	2	Liver: 570.xx-573.xx	B251, K700, K7010, K7011, K702, K7030, K7031, K7040, K7041, K709, K710, K7110, K7111, K712, K713, K714, K7150, K7151, K716, K717, K718, K719, K7200, K7201, K7210, K7211, K7290, K7291, K730, K731, K732, K738, K739, K740, K741, K742, K743, K744, K745, K7460, K7469, K750, K751, K752, K753, K754, K7581, K7589, K759, K760, K761, K762, K763, K764, K765, K766, K767, K7681, K7689, K769, K77
Stroke	1 point	History of stroke V12.54, 433.xx-436.xx	G450, G451, G452, G458, G459, G460, G461, G462, I6300, I63011, I63012, I63013, I63019, I6302, I63031, I63032, I63033, I63039, I6309, I6310, I63111, I63112,

HAS-BLED	Point	ICD-9 Codes	ICD-10 Codes
			I63113, I63119, I6312, I63131, I63132, I63133, I63139, I6319, I6320, I63211, I63212, I63213, I63219, I6322, I63231, I63232, I63233, I63239, I6329, I6330, I63311, I63312, I63313, I63319, I63321, I63322, I63323, I63329, I63331, I63332, I63333, I63339, I63341, I63342, I63343, I63349, I6339, I6340, I63411, I63412, I63413, I63419, I63421, I63422, I63423, I63429, I63431, I63432, I63433, I63439, I63441, I63442, I63443, I63449, I6349, I6350, I63511, I63512, I63513, I63519, I63521, I63522, I63523, I63529, I63531, I63532, I63533, I63539, I63541, I63542, I63543, I63549, I6359, I636, I638, I639, I6501, I6502, I6503, I6509, I651, I6521, I6522, I6523, I6529, I658, I659, I6601, I6602, I6603, I6609, I6611, I6612, I6613, I6619, I6621, I6622, I6623, I6629, I663, I668, I669, I67841, I67848, Z8673

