	0D1A8ZH	Bypass Jejunum to Cecum, Via Natural or Artificial Opening Endoscopic
	0D1A8ZK	Bypass Jejunum to Ascending Colon, Via Natural or Artificial Opening Endoscopic
	0D1A8ZL	Bypass Jejunum to Transverse Colon, Via Natural or Artificial Opening Endoscopic
	0D1A8ZM	Bypass Jejunum to Descending Colon, Via Natural or Artificial Opening Endoscopic
	0D1A8ZN	Bypass Jejunum to Sigmoid Colon, Via Natural or Artificial Opening Endoscopic
	0D1A8ZP	Bypass Jejunum to Rectum, Via Natural or Artificial Opening Endoscopic
	0D1B0ZB	Bypass Ileum to Ileum, Open Approach
	0D1B0ZH	Bypass Ileum to Cecum, Open Approach
	0D1B0ZK	Bypass Ileum to Ascending Colon, Open Approach
	0D1B0ZL	Bypass Ileum to Transvers e Colon, Open Approach
	0D1B0ZM	Bypass Ileum to Descending Colon, Open Approach
	0D1B4ZN	Bypass Ileum to Sigmoid Colon, Percutaneous Endoscopic Approach
	0D1B4ZP	Bypass Ileum to Rectum, Percutaneous Endoscopic Approach
	0D1B4ZQ	Bypass Ileum to Anus, Percutaneous Endoscopic Approach
	0D1B8ZB	Bypass Ileum to Ileum, Via Natural or Artificial Opening Endoscopic
	0D1B8ZH	Bypass Ileum to Cecum, Vi a Natural or Artificial Opening Endoscopic

Type	Codes	Description
	0D1B8ZK	Bypass Ileum to Ascending Colon, Via Natural or Artificial Opening Endoscopic
	0D1B8ZL	Bypass Ileum to Transverse Colon, Via Natural or Artificial Opening Endoscopic
	0D1B8ZM	Bypass Ileum to Descending Colon, Via Natural or Artificial Opening Endoscopic
	0D1B8ZN	Bypass Ileum to Sigmoid Colon, Via Natural or Artificial Opening Endoscopic
	0D1B8ZP	Bypass Ileum to Rectum, Via Natural or Artificial Opening Endoscopic
	0D1B8ZQ	Bypass Ileum to Anus, Via Natural or Artificial Opening Endoscopic

Table 10. Charlson Comorbidity Index Score Calculation

Condition	ICD-9 Code(s)	ICD-10 Code(s)	Point
Myocardial Infarction	410.xx; 412.xx	I21, I22, I252	1
Congestive Heart Failure	428.xx	I43, I50, I099, I110, I130, I132, I255, I420, I425, I426, I427, I428, I429, P290	1
Peripheral vascular disease	441.xx; 443.9x; 785.4x; v43.4x, procedure : 38.48	I70, I71, I731, I738, I739, I771, I790, I792, K551, K558, K559, Z958, Z959	1
Cerebrovascular disease	430.xx-438.99 Modified to remove 430.xx-432.xx	G45, G46, I60, I61, I62, I63, I64, I65, I66, I67, I68, I69, H340	1
Dementia	290.xx	F00, F01, F02, F03, G30, F051, G311	1
Chronic obstructive pulmonary disease	490.xx-496.99; 500.xx-505.99; 506.4x	J40, J41, J42, J43, J44, J45, J46, J47, J60, J61, J62, J63, J64, J65, J66, J67, I278, I279, J684, J701, J703	1

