Rheumatologic disease	710.0x-710.19; 710.4x-; 714.0x-714.29; 714.81; 725.xx	M05, M32, M33, M34, M06, M315, M351, M353, M360	1
Peptic ulcer disease	531.0x-531.79; 532.4x-532.79; 533.4x-533.79; 534.0x-534.79; 531.9x; 532.9x; 533.9x; 534.9x Modified to remove: 531.00, 531.01, 531.20, 531.21, 531.40, 531.41, 531.60, 531.61 532.40, 532.41, 532.60, 532.61 533.40, 533.41, 533.60, 533.61, 534.00, 534.01, 534.20, 534.21, 534.40, 534.41, 534.60, 534.61	K25, K26, K27, K28	1

Condition	ICD-9 Code(s)	ICD-10 Code(s)	Point
Mild liver disease	571.2x; 571.4x-571.69	B18, K73, K74, K700, K701, K702, K703, K709, K717, K713, K714, K715, K760, K762, K763, K764, K768, K769, Z944	1
Diabetes (mild to moderate)	250.0x-250.39, 250.7x	E100, E101, E106, E108, E109, E110, E111, E116, E118, E119, E120, E121, E126, E128, E129, E130, E131, E136, E138, E139, E140, E141, E146, E148, E149	1
Diabetes + complications	250.4x-250.69	E102, E103, E104, E105, E107, E112, E113, E114, E115, E117, E122, E123, E124, E125, E127, E132, E133, E134, E135, E137, E142, E143, E144, E145, E147	2
Hemiplegia or paraplegia	342.xx; 344.1x	G81, G82, G041, G114, G801, G802, G830, G831, G832, G833, G834, G839	2
Renal disease	582.xx; 583.0x-583.79; 585.xx-586.99; 588.xx	N18, N19, N052, N053, N054, N055, N056, N057, N250, I120, I131, N032, N033, N034, N035, N036, N037, Z490, Z491, Z492, Z940, Z992	2
Any malignancy, including lymphoma and leukemia	140.xx-172.99; 174.xx-195.99; 200.xx-208.99	C00, C01, C02, C03, C04, C05, C06, C07, C08, C09, C10, C11, C12, C13, C14, C15, C16, C17, C18, C19, C20, C21, C22, C23, C24, C25, C26, C30, C31, C32, C33, C34, C37, C38, C39, C40, C41, C43, C45, C46, C47, C48, C49, C50, C51, C52, C53, C54, C55, C56, C57, C58, C60, C61, C62, C63, C64, C65, C66, C67, C68, C69, C70, C71, C72, C73, C74, C75, C76, C81, C82, C83, C84, C85, C88, C90, C91, C92, C93, C94, C95, C96, C97	2
Moderate/severe liver disease	456.0x-456.29; 572.2x-572.89 Modified to remove: 456.0x, 456.20	K704, K711, K721, K729, K765, K766, K767, I850, I859, I864, I982	3
Metastatic solid tumor	196.xx-199.99	C77, C78, C79, C80	6
AIDS	042.xx-044.99	B20, B21, B22, B24	6

Table 11. Baseline Comorbidities

Covariates	ICD-9-CM/CPT/HCPCS Codes	ICD-10-CM Codes
History Stroke/SE	Same as the outcome stroke/SE (Table 12)	Same as the outcome stroke/SE (Table 12)
History of Bleeding	Same as the outcome major bleeding (Table 12)	Same as the outcome major bleeding (Table 12)

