Transient ischemic attack (TIA)	435.x	G458, G459, Z8673
Coronary artery disease	410.xx-414.xx	I200, I201, I208, I209, I2101, I2102, I2109, I2111, I2119, I2121, I2129, I213, I214, I220, I221, I222, I228, I229, I240, I241, I248, I249, I2510, I25110, I25111, I25118, I25119, I252, I253, I2541, I2542, I255, I256, I25700, I25701, I25708, I25709, I25710, I25711, I25718, I25719, I25720, I25721, I25728, I25729, I25730, I25731, I25738, I25739, I25750, I25751, I25758, I25759, I25760, I25761, I25768, I25769, I25790, I25791, I25798, I25799, I25810, I25811, I25812, I2582, I2583, I2584, I2589, I259
Anemia and coagulation defects	280.xx-286.xx	D50-D53, D55-D59, D60-D69,

Table 12. Clinical Outcomes

Outcome Variables		ICD-9-CM/Procedure Codes	ICD-10-CM Codes/Procedure Codes
Stoke/ SE	Hemorrhagic Stroke	430.xx-432.xx Cases will be excluded if traumatic brain injury (ICD-9: 800-804, 850-854) was present during hospitalization.	I6000, I6001, I6002, I6010, I6011, I6012, I602, I6030, I6031, I6032, I604, I6050, I6051, I6052, I606, I607, I608, I609, I610, I611, I612, I613, I614, I615, I616, I618, I619; Cases will be excluded according to Table 12.
	Ischemic Stroke	433.x1, 434.x1, 436	I6300, I63011, I63012, I63013, I63019, I6302, I63031, I63032, I63033, I63039, I6309, I6310, I63111, I63112, I63113, I63119, I6312, I63131, I63132, I63133, I63139, I6319, I6320, I63211, I63212, I63213, I63219, I6322, I63231, I63232, I63233, I63239, I6329, I6330, I63311, I63312, I63313, I63319, I63321, I63322, I63323, I63329, I63331, I63332, I63333, I63339, I63341, I63342, I63343, I63349, I6339, I6340, I63411, I63412, I63413, I63419, I63421, I63422, I63423, I63429, I63431, I63432, I63433, I63439, I63441, I63442, I63443, I63449, I6349, I6350, I63511, I63512, I63513, I63519, I63521, I63522, I63523, I63529, I63531, I63532, I63533, I63539, I63541, I63542, I63543, I63549, I6359, I636, I638, I639, I6789
	Systemic	444.x, 445.x	I7401, I7409, I7410, I7411, I7419, I742, I743,

Outcome Variables		ICD-9-CM/Procedure Codes	ICD-10-CM Codes/Procedure Codes
	Embolism		I744, I745, I748, I749, I75011, I75012, I75013, I75019, I75021, I75022, I75023, I75029, I7581, I7589

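### The History of Stroke/SE covariate uses only the outcome codes in a 6-month baseline and omits the history and sequela codes the plan uses elsewhere, so it under-records older stroke

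*Combined protocol and SAP*

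**What the plan says.** Section 9.3, Table 1 lists the covariate among the comorbidities: "The following comorbid conditions will be flagged in baseline: History of stroke/SE". The window is given at the start of that section: "Baseline variables during the 6 months prior to, and on, the index date will be measured". No longer lookback is stated for this row.

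In the Appendix (Section 17.1), Table 11 gives the same definition in its ICD-9 and ICD-10 columns: "Same as the outcome stroke/SE (Table 12". For ischemic stroke, the ICD-9 list in Table 12 is "433.x1, 434.x1, 436". The full outcome list is 430-432, 433.x1, 434.x1, 436, 444 and 445 in ICD-9, and I60, I61, I63, I67.89, I74 and I75 in ICD-10.

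Other baseline items are built differently. The HAS-BLED stroke item (Table 7) reads "History of stroke V12.54, 433.xx-436.xx" in ICD-9 and includes Z86.73 in ICD-10. The Charlson cerebrovascular item (Table 10) is "430.xx-438.99 Modified to remove 430.xx-432.xx" in ICD-9 and includes I69 in ICD-10.

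On diagnosis position, the baseline rule is broader than the outcome rule. For baseline, "Baseline variables will be evaluated using codes in any position unless noted otherwise". For the outcome, "Stroke/SE will be identified using hospital claims which had a stroke/SE diagnosis code as the primary diagnosis code".

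**The concern.** The row is labelled as history but is built from the codes that define the study's own event. An older stroke that appears during baseline only as a history or sequela code does not set it. Table 7 itself labels V12.54 as history of stroke, so the row omits a code that the plan recognises as meaning exactly that.

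Two uses are affected. Aim 1 will report the row as a baseline characteristic, and readers will take it as prior stroke. The row is also a natural candidate for the propensity model behind the stroke/SE and net clinical benefit comparisons. Section 9.7.1 treats a covariate as balanced below a 10% standardized difference and adds only unbalanced variables to the Cox model. A flag that under-records can pass that check while true prior stroke remains unequal, and no adjustment would then follow.

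**Working it through.** **Step 1. Code lists side by side.** Each cell says whether the code is in the item.

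| Baseline item | V12.54 | Z86.73 | 438 | I69 |
|---|---|---|---|---|
| History of Stroke/SE (Table 11, via Table 12) | no | no | no | no |
| CHADS2 stroke (Table 5) | yes | no | no | no |
| CHA2DS2-VASc stroke (Table 6) | yes | no | no | no |
| HAS-BLED stroke (Table 7) | yes | yes | no | no |
| Charlson cerebrovascular (Table 10) | no | no | yes | yes |
| TIA row (Table 11) | no | yes | no | no |

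The omission is in both coding systems. A Z86.73 record sets the TIA row but not the stroke row. A patient with only a sequela code (438 or I69) shows up in Charlson and in no other item here.

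**Step 2. Can the share missed be computed?** The documents give no prevalence, timing or coding pattern for prior stroke. Assume that outcome codes appear only at the acute event.

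- Past strokes spread evenly over Y years: share missed = 1 - 0.5/Y. For Y = 1, 2, 5 and 10 this is 50%, 75%, 90% and 95%.
- A share f falling just before anticoagulant start, the rest spread over 5-10 years: share missed = (1 - f)(1 - 0.5/Y). For f = 25%, 50% and 75% this is 68-71%, 45-48% and 22-24%.

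The answer depends on the assumption.

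**Step 3. Possible effect on the hazard ratio.** All inputs are assumptions: true prior stroke p of 12% on apixaban and 15% or 18% on warfarin; detection s of 25% or 50% with no false positives; stroke risk ratio R of 2 or 3; the flag is the only stroke-history covariate in the model.

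- Undetected prevalence among patients with flag 0: q = p(1 - s)/(1 - ps).
- Weighting equalises the flag prevalence at F, the average of the two arms.
- Bias factor = [F·R + (1 - F)(1 + (R - 1)q_apixaban)] / [F·R + (1 - F)(1 + (R - 1)q_warfarin)].

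Worked case, 18% vs 12%, s = 25%, R = 3:

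- Flag prevalence is 4.5% vs 3.0%, so F = 0.0375.
- q_warfarin = 0.135/0.955 = 0.1414 and q_apixaban = 0.09/0.97 = 0.0928.
- Factor = (0.1125 + 0.9625 × 1.1856)/(0.1125 + 0.9625 × 1.2827) = 1.2536/1.3471 = 0.931.
- True prior stroke after balancing is 17.4% vs 12.7%, a standardized difference of 13.1%. The flag's own difference before weighting is only 7.9%, already inside the 10% limit.

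| Warfarin vs apixaban | Detected | Residual standardized difference | Factor, R = 2 | Factor, R = 3 |
|---|---|---|---|---|
| 18% vs 12% | 25% | 13.1% | 0.960 | 0.931 |
| 18% vs 12% | 50% | 9.1% | 0.972 | 0.951 |
| 15% vs 12% | 25% | 6.8% | 0.980 | 0.964 |
| 15% vs 12% | 50% | 4.7% | 0.986 | 0.975 |

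Applied to the planning hazard ratio of 0.63 (Section 9.5), the extremes give 0.63 × 0.931 = 0.59 and 0.63 × 0.986 = 0.62. With equal undetected prevalence in both arms the factor is 1.00.

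**The case against.** Four arguments can be made for the plan.

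1. Baseline codes count in any position, so an outcome code carried onto a later claim sets the flag even for an old stroke. This is correct. It is one reason the share missed is unknown, but it does nothing for a patient whose only record is a history or sequela code.
2. Every omitted code already feeds at least one other baseline variable. This is also correct, and it reduces the possible bias if those variables enter the model. The protection is partial. The propensity covariates are left to clinical rationale in Section 9.7.1, and Charlson is named only as a possible covariate for the matching sensitivity analysis. The two CHADS-type scores lack Z86.73 and I69 in ICD-10. The scores also mix stroke with other items, so balance on a score is not balance on stroke.
3. The score items are broader constructs: their ICD-9 ranges include 435 (TIA) and their ICD-10 lists include I65 and I66. A score point with the flag at 0 is therefore not in itself a contradiction. That stands. The point rests on the missing history codes, not on every such disagreement.
4. In three of the four prevalence and detection scenarios the residual imbalance is below the plan's own 10% limit. That stands too, and the possible bias is modest.

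A reader might go further and infer that most patients with an older stroke are reported and balanced as having none. The documents do not support that. They contain no figure from which a majority could be derived, and the statement would concern this one row, not the whole covariate set.

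**Conclusion.** The defect is in the definition and can be read from the tables. The row captures recent outcome-coded events, omits the history and sequela codes used elsewhere in the plan, and so under-records older stroke. For a patient whose only baseline record is V12.54 or Z86.73, it reads 0 while HAS-BLED counts a stroke.

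The effect on the results is conditional. Under the assumed prevalences, detection and risk ratios, the stroke hazard ratio could be multiplied by about 0.93 to 0.99, in favour of apixaban, if warfarin patients have more undetected prior stroke. A reader might infer that the hazard ratios are biased toward apixaban as planned. The documents show neither the size nor the direction, because they give no prior-stroke prevalence by arm and do not fix the propensity model. The mislabelled Aim 1 row does not depend on any of these assumptions.

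**What to change.** - Relabel the current row as recent stroke/SE (outcome codes, 6 months).
- Add a prior stroke/TIA flag using V12.54 and 438.xx in ICD-9 and Z86.73 and I69.x in ICD-10, in any position.
- Reconcile the new flag with the TIA row, which already holds Z86.73, so that it is clear which row or rows a Z86.73 record sets.
- Report both stroke flags in the Aim 1 baseline tables.
- Name both in the propensity model and apply the 10% balance check to both.

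The cost is one extra row in Table 11, from codes the plan already handles, with no new data. The new flag also captures prior TIA and overlaps the TIA row, hence its label. It keeps the 6-month window, so a patient with no stroke-related code in that window is still missed.
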